## **Human Subjects Procedures**

### **a. Human Subjects Involvement, Characteristics, and Design**

Study design: This study will examine heart rate variability (HRV), endothelial function (FMD), and overnight blood pressure in response to acute moderate aerobic exercise followed by leg heating in 42°C water (Ex + HT), aerobic exercise followed by a sham leg immersion in 33°C water (Ex), leg heating alone in 42°C water (HT), or control conditions (no exercise or heat exposure) in adults with elevated blood pressure. The study will consist of four trials, administered in a randomized, counterbalanced fashion, with all participants completing all treatments, with at least 5 days between each trial.

Subject population: The subject population will be adults with elevated blood pressure (defined as resting blood pressure >120/80 mmHg; not diagnosed hypertension). Inclusion criteria for all subjects will be age 18-50, BMI between 18-39.9, not taking any anti-hypertensive medications, no history of heat illness. Blood pressure will be measured at the screening visit and volunteers must have duplicate resting blood pressures >120/80 (taken after 15 minutes of quiet rest in the lab) in order to qualify for the study. These inclusion criteria, including age range, were selected to minimize the risk of acute cardiovascular events during exercise. All subjects must be capable of walking 30 min at a moderate intensity on a treadmill. An effort will be made to recruit men and women in equal numbers, and for the diversity of the subject pool to match the local community.

Research sites: This is a single-site study and all research activities will be conducted at Providence College.

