### **b. Study Procedures, Materials, and Potential Risks**

Volunteers will report to the lab for an introductory visit and screening 24 hours prior to their first study day. After a review of study procedures and resting blood pressure measurement, they will be instrumented with an ambulatory blood pressure cuff which will take hourly measurements for the 24 hours preceding their first study day for familiarization with the equipment.

Upon arrival for testing the following afternoon, weight and height will be assessed, and volunteers will be instrumented with a 3-lead ECG and a beat-by-beat blood pressure monitor before lying supine in a room-temperature lab for 15 minutes prior to baseline (pre-intervention) measures of heart rate, heart rate variability (HRV), blood pressure, and flow-mediated dilation (FMD) of the brachial artery (described below). After baseline measures, volunteers will complete the daily protocol, consisting of either exercise + heat (Ex + HT), exercise + sham immersion (Ex) or heat alone (HT). On the control day, only baseline measures will be taken and the volunteer will be instrumented with the ambulatory blood pressure cuff with instructions to refrain from exercise or heat exposure during the 24h measurement.

Blood Pressure measurement: Blood pressure will be measured regularly in the lab for safety monitoring using a clinical-grade automated blood pressure cuff. Ambulatory blood pressure will be measured for a 24 hour period following each of the four conditions: control (no exercise or heat), Exercise, Heat Therapy, and combined Exercise and Heat Therapy. The Welch-Allyn

ambulatory monitor inflates once per hour and stored blood pressure readings for download by the research staff.

Heart Rate Variability (HRV): HRV will be measured during supine rest on a padded exam table. Participants will be instrumented with three foam stickers on the shoulders and hip which connect to a device that records and analyses heart rhythm (Finapres Nova). They will be asked to breathe to a metronome (paced breathing) for a period of 10 minutes to ensure adequate data collection.

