**Potential Risks to Participants:** The proposed study will utilize cardiovascular monitoring techniques with minimal risks. The exercise session will be supervised within the Health & Human Performance lab with heart rate and perceived exertion continuously monitored by study staff. Exercise will be stopped in the event of difficulty breathing, chest pain, if heart rate exceeds 90% of age-predicted maximum, or if they feel they cannot continue. There is a risk of slight muscle soreness following exercise, but this is uncommon given the mode (walking) and duration (30 minutes).

Additional measures include blood pressure, tympanic temperature, blood flow, and heart rate variability (HRV). Insertion of the tympanic temperature sensor in the ear and inflation of the blood pressure cuff may cause mild discomfort (common). The inflation of the cuff on the forearm for flow-mediated dilation for 5 minutes may cause mild to moderate discomfort (sense of pressure

at the site of inflation and mild tingling in the fingers). There is also a chance of irritation of the skin where foam sticker electrodes are applied to measure heart rhythm (less common). The immersion of the lower limbs in hot water may cause mild discomfort, including a warm sensation and initiation of the sweating response (common). During heating, an increase in heart rate, increase in core temperature, and small decrease in blood pressure are also likely (common). Heart rate, blood pressure, and temperature will be monitored throughout heating and the subject will be removed from the leg bath if heart rate increases more than 50 beats per minute, tympanic temperature exceeds 39.5°C, blood pressure falls more than 10 mmHg, or if the subject reports any heat-related symptoms (uncomfortably hot, light-headed, nauseated, heart racing). These potential risks are uncommon given the small amount of body surface area being heated. Water temperature will be continuously monitored and set at a level (40-42°C) well below the threshold for burning (47°C). Ice and fans will be on hand to initiate rapid cooling if needed.

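### Eligibility sets a measured blood-pressure floor and a diagnosis-status restriction but no measured ceiling, and no baseline reading would postpone a session

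*Combined protocol and SAP*

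**What the plan says.** All references are to the combined protocol and SAP.

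- **Entry** (section a, Human Subjects Involvement, Characteristics, and Design, Subject population). The population is "defined as resting blood pressure >120/80 mmHg; not diagnosed hypertension". At screening, "volunteers must have duplicate resting blood pressures >120/80 (taken after 15 minutes of quiet rest in the lab"). Anti-hypertensive medication is not allowed. The section says the inclusion criteria "were selected to minimize the risk of acute cardiovascular events during exercise".
- **Timing** (section b, Study Procedures, Materials, and Potential Risks). Screening comes one day before the first session: "Volunteers will report to the lab for an introductory visit and screening 24 hours prior to their first study day".
- **Study day** (same section). Pressure is measured at rest, and then: "After baseline measures, volunteers will complete the daily protocol". The Control day has baseline measures and the ambulatory cuff only. The section adds: "Blood pressure will be measured regularly in the lab for safety monitoring using a clinical-grade automated blood pressure cuff".
- **Stopping** (same section, Potential Risks to Participants). Exercise stops for symptoms, a heart rate above 90% of the age-predicted maximum, or inability to continue. The leg bath stops if, among other triggers, "blood pressure falls more than 10 mmHg".
- **General protections** (section 2b, Protections Against Risk). Criteria exist for stopping exercise or heating when blood-pressure responses are unusual; no values are given.
- **Very high readings** (Incidental Findings). Staff make no diagnosis, share the result and suggest primary care follow-up.
- **Exclusion criteria** (section 2a, Informed Consent and Assent). They are mentioned but not listed.

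**The concern.** Volunteers are selected for high pressure and are all untreated. In such a sample the upper end of the pressure range needs a rule, and the readable text has none. The diagnosis restriction depends on whether someone has already been told they have hypertension. It does not act on the number the lab has just measured, and staff are told not to diagnose.

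What is at stake is participant safety. A volunteer with very high, unrecognised pressure satisfies every listed criterion and moves from baseline measures to treadmill walking or hot immersion. Screening may be only a day earlier, so the suggested follow-up need not have happened. The lab already measures pressure at the points where a decision is needed, but the plan attaches no decision about starting to those measurements.

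**Working it through.** The plan has no figure to reproduce, because the point is that a rule is absent. The check has three steps.

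**1. Every blood-pressure value in the documents**

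| Value | Where | Purpose | Upper limit for a participant? |
|---|---|---|---|
| >120/80 mmHg | Subject population | Entry floor | No |
| Fall of >10 mmHg | Potential Risks to Participants | Removal from leg bath | No, opposite direction |
| 250 mmHg | Flow-mediated dilation procedure | Forearm cuff inflation | No, a device setting |

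**2. A hypothetical volunteer followed through the text**

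Take an untreated adult within the age and BMI limits, never diagnosed, whose duplicate screening readings are both very high.

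- Floor: met.
- Not diagnosed: met, since it is a status and staff make no diagnosis.
- No medication: met.
- Very high reading: disclosed, follow-up suggested. The text does not say whether sessions continue.
- Next day's baseline pressure: measured, with no hold value.
- During exercise: the listed stops contain no pressure value.
- During heating: the numeric pressure stop concerns a fall.
- Unusual blood-pressure responses: covered in general terms, but as a reason to stop a session, not a condition for starting one.

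No written rule keeps this volunteer from starting.

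**3. Size of the exposure**

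Inputs: 10 men + 10 women = 20 participants (Statistical Design and Power); four conditions each, of which Ex and Ex + HT use the treadmill (section a).

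- Study visits: 20 × 4 = 80.
- Treadmill sessions: 20 × 2 = 40.
- Heat-alone sessions: 20 × 1 = 20.
- Control visits: 20 × 1 = 20.
- First study day, assuming the four conditions are spread evenly over it: 20 × 3/4 = 15 participants have an active session about 24 hours after screening, and 20 × 2/4 = 10 of them are on the treadmill.

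These are counts of sessions, not of risk. How many readings would be high depends on a distribution that the documents do not give.

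**4. Whether the rule should apply on Control days**

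Suppose the hold applied only to active sessions. Those days would then go ahead only when that day's pressure was below the ceiling, while Control days would go ahead at any pressure. Active days would be selected for lower pressure, which would tilt mean nocturnal blood pressure, the Aim 1 primary outcome, towards the interventions. Keeping the assigned order would not remove this. The size would depend on how many sessions were held, which is unknown. Applying the same rule on all four days removes the difference in selection.

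**The case against.** **A limit may exist outside the visible text.** Exclusion criteria are mentioned but not listed, section 2b refers to criteria already in place and to a separate emergency plan, and some pages are missing from the copy reviewed. This stands. A reader might infer that the sponsor has no ceiling at all; the documents do not support that. They support only that none is stated where eligibility and the start of a session are described.

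**The intended population is milder than the floor alone suggests.** The diagnosis restriction sits beside the floor, and section 4 (Importance of the Knowledge to be Gained) separates elevated pressure from diagnosable hypertension. This is fair as to intent, but intent does not exclude an undiagnosed volunteer with a very high reading.

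**The exposure is modest and supervised.** Participants are 18 to 50. The walking bout is at 55–60% of heart rate reserve, chosen on evidence in hypertensive subjects. Sessions are supervised, with symptom and heart-rate stops, and pressure is checked every 5 minutes during immersion. All of this stands and lowers the concern. It does not imply that any starting pressure is acceptable, and stopping rules act only once a session has begun.

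**Heat-alone sessions carry little hypertensive hazard.** This stands: the plan expects heating to lower pressure slightly. A reader might count all 60 active sessions (40 + 20) as equally exposed; the treadmill sessions are the relevant number.

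**No threshold can be derived from the documents.** This stands. The range offered under the fix is an assumption. Its upper end would admit pressures well above the population the plan describes, which is a reason for the sponsor to consider the lower end.

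**Conclusion.** The point holds for the visible text. Eligibility has a measured floor and a diagnosis-status restriction but no measured ceiling; no baseline value postpones a session; and the only written response to very high pressure is disclosure and suggested follow-up. This is a gap in a safety rule whose stated purpose is to limit cardiovascular events during exercise, so the sponsor should correct it before enrolment.

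The main exposure is 40 treadmill sessions, with about 10 of the 20 participants reaching the treadmill on the first study day if the order is evenly balanced. A reader might infer that harm is likely, or that some number of participants would be over a limit. The documents give no basis for either, and no probability is claimed.

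Confidence is medium, because an unlisted exclusion criterion could already contain a limit.

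**What to change.** If a ceiling already exists, state it under Subject population and in the study-day procedures. If not:

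1. **Subject population.** Require both duplicate screening readings to be above the floor and below a ceiling set by the sponsor. An assumed working range is 160/100 to 180/110 mmHg.
2. **Study Procedures.** Take a resting cuff reading at baseline on all four study days, Control included. If it is at or above the ceiling, repeat once after 5 minutes. Proceed if the repeat is below; postpone the visit, keeping its place in the assigned order, if it is not.
3. **Incidental Findings.** After a confirmed reading at or above the ceiling, require primary care clearance before further sessions.
4. **Statistical Design and Power.** State how a participant who cannot complete all four conditions is analysed.

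The existing stopping rules stay as they are.

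**Cost.**

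- *Readings.* One or two cuff readings per visit: 80 × 1 = 80 to 80 × 2 = 160 over the study. The plan sets up a beat-by-beat monitor before baseline and does not say that the baseline value is a cuff reading, so the first reading may be an addition. The cuff is already in the lab.
- *Schedule.* Postponement fits, because the plan sets only a minimum gap ("with at least 5 days between each trial").
- *Recruitment and completeness.* A few volunteers may be excluded. Some crossovers may be left incomplete, for instance if referral leads to medication. Under a complete-case repeated-measures ANOVA, each such loss removes 1/20 = 5% of the sample, or 1/10 = 10% of one sex. The largest minimum stated in the power section is 10, so the pooled comparison has 20 − 10 = 10 participants in reserve; the comparison between sexes has no stated reserve.

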### **b. Study Procedures, Materials, and Potential Risks**

Volunteers will report to the lab for an introductory visit and screening 24 hours prior to their first study day. After a review of study procedures and resting blood pressure measurement, they will be instrumented with an ambulatory blood pressure cuff which will take hourly measurements for the 24 hours preceding their first study day for familiarization with the equipment.

Upon arrival for testing the following afternoon, weight and height will be assessed, and volunteers will be instrumented with a 3-lead ECG and a beat-by-beat blood pressure monitor before lying supine in a room-temperature lab for 15 minutes prior to baseline (pre-intervention) measures of heart rate, heart rate variability (HRV), blood pressure, and flow-mediated dilation (FMD) of the brachial artery (described below). After baseline measures, volunteers will complete the daily protocol, consisting of either exercise + heat (Ex + HT), exercise + sham immersion (Ex) or heat alone (HT). On the control day, only baseline measures will be taken and the volunteer will be instrumented with the ambulatory blood pressure cuff with instructions to refrain from exercise or heat exposure during the 24h measurement.

Blood Pressure measurement: Blood pressure will be measured regularly in the lab for safety monitoring using a clinical-grade automated blood pressure cuff. Ambulatory blood pressure will be measured for a 24 hour period following each of the four conditions: control (no exercise or heat), Exercise, Heat Therapy, and combined Exercise and Heat Therapy. The Welch-Allyn

ambulatory monitor inflates once per hour and stored blood pressure readings for download by the research staff.

Heart Rate Variability (HRV): HRV will be measured during supine rest on a padded exam table. Participants will be instrumented with three foam stickers on the shoulders and hip which connect to a device that records and analyses heart rhythm (Finapres Nova). They will be asked to breathe to a metronome (paced breathing) for a period of 10 minutes to ensure adequate data collection.

Flow-mediated dilation (FMD): While resting supine on a padded exam table, participants will be asked to extend their right arm so that we can obtain an ultrasound image of the brachial artery. We will also instrument the participant with an inflatable cuff placed just below the elbow. Once a quality image of the artery is obtained, we will ask the participant to stay still while we record a baseline measure of artery diameter and blood flow before inflating the cuff to 250mmHg for a period of 5 minutes. After five minutes have passed, the cuff pressure will be released, allowing for a rapid increase in blood flow through the brachial artery to reperfuse the forearm. We will continue to record blood vessel diameter and blood flow for 3 minutes after cuff release for analysis of % dilation of the brachial artery and changes in blood flow and shear patterns.

Exercise Intervention: During Exercise (Ex) or combined exercise and heat therapy trials (Ex + HT), the exercise session will consist of 30 minutes of treadmill walking at 55-60% of heart rate reserve (calculated based on resting heart rate measurement taken in the lab and age-predicted maximum heart rate). The treadmill will initially be set at 2% grade and 2.5 miles per hour, and adjusted in the first five minutes to achieve the target heart rate. Heart rate will be monitored continuously, and RPE will be assessed every five minutes. This exercise protocol was selected because it has been shown to produce reductions in systolic and diastolic blood pressure in hypertensive subjects while minimizing risk of adverse events during exercise. This exercise protocol is also supported by the American College of Sports Medicine guidelines for individuals with hypertension.

Leg heating: Following exercise, participants will be seated in a chair for 45 minutes with their legs immersed to mid-calf in either lukewarm (33°C; sham leg immersion in Ex trial) or hot (42°C, Ex + HT trial) while heart rate, blood pressure, and tympanic temperature are monitored every 5 minutes. For the standalone heat therapy trial (HT), participants will complete the 45 minute hot (42°C) leg immersion with no prior exercise. Heart rate, blood pressure, and tympanic temperature will be monitored every 5 minutes, and subjects will have free access to fluids.

**Potential Risks to Participants:** The proposed study will utilize cardiovascular monitoring techniques with minimal risks. The exercise session will be supervised within the Health & Human Performance lab with heart rate and perceived exertion continuously monitored by study staff. Exercise will be stopped in the event of difficulty breathing, chest pain, if heart rate exceeds 90% of age-predicted maximum, or if they feel they cannot continue. There is a risk of slight muscle soreness following exercise, but this is uncommon given the mode (walking) and duration (30 minutes).

Additional measures include blood pressure, tympanic temperature, blood flow, and heart rate variability (HRV). Insertion of the tympanic temperature sensor in the ear and inflation of the blood pressure cuff may cause mild discomfort (common). The inflation of the cuff on the forearm for flow-mediated dilation for 5 minutes may cause mild to moderate discomfort (sense of pressure

at the site of inflation and mild tingling in the fingers). There is also a chance of irritation of the skin where foam sticker electrodes are applied to measure heart rhythm (less common). The immersion of the lower limbs in hot water may cause mild discomfort, including a warm sensation and initiation of the sweating response (common). During heating, an increase in heart rate, increase in core temperature, and small decrease in blood pressure are also likely (common). Heart rate, blood pressure, and temperature will be monitored throughout heating and the subject will be removed from the leg bath if heart rate increases more than 50 beats per minute, tympanic temperature exceeds 39.5°C, blood pressure falls more than 10 mmHg, or if the subject reports any heat-related symptoms (uncomfortably hot, light-headed, nauseated, heart racing). These potential risks are uncommon given the small amount of body surface area being heated. Water temperature will be continuously monitored and set at a level (40-42°C) well below the threshold for burning (47°C). Ice and fans will be on hand to initiate rapid cooling if needed.

There is a remote (uncommon) risk of breach of confidentiality. Maintaining research volunteers' privacy and keeping personal identifiers confidential is important to the study staff. All research activity including subject screening and data collection will be performed and stored at Providence College. Subject names, contact information, health history, and other information that can be traced back to the subject will be kept securely and separately from data collected for the study. Personal information will be kept in a locked office and away from data. Collected data will have the subject's identification code and some computer software used to collect data (LabChart) will have the date and time marked on the file. Protocol sheets used during data collection will only have the subject's ID. The tests will have a subject ID and may contain other pertinent information needed to clinically evaluate the test, such as age, gender, and blood pressure measurement. All data will be stored in a secure server and encrypted hard drives. All key personnel have completed education on the use of human subjects (CITI, Good Clinical Practices [GCP] training) in compliance with NIH regulations.

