### **Statistical Design and Power**

This study investigates the potential for heat therapy to supplement or augment exercise for blood pressure reduction. To estimate expected effect sizes, we calculated standardized mean differences in our key outcomes using pilot data from our healthy participants:  $d = (x_{baseline} - x_{intervention})/S$ , where x represents the baseline (no intervention) and post-treatment (combined exercise and heat) values and S is the standard deviation. This effect size calculation reflects differences in outcome means anticipated for the proposed study. Taking into consideration the relatively low costs and low risks of hot water leg immersion, these differences are not only statistically significant, but also clinically meaningful at the individual and population levels.

**Primary analyses:** The primary outcome variable for Specific Aim 1 is mean nocturnal blood pressure. Using previous data from our lab in healthy men and women, a power analysis indicates that a minimum of 8 participants should be required to see changes between intervention and control treatments using a repeated-measures ANOVA design. For Specific Aim 2, our primary outcome variable is the time domain analysis of Heart Rate Variability (standard deviation of normal to normal R-R intervals; SDNN). Using pilot data from a study examining post-exercise hot or cold water immersion, a minimum of 10 participants is required to see differences in HRV between treatments using a repeated-measures ANOVA design. For Specific Aim 3, data from existing literature examining endothelial function (flow-mediated dilation) before and after a single bout of exercise in individuals with hypertension indicates that a minimum of 10 participants would be required to see significant differences in % dilation (the primary outcome of FMD analysis) between treatments. Given that there may be sex differences in the magnitude, timing, or mechanisms of blood pressure responses to exercise and heating, we plan to recruit sufficient numbers (10 men, 10 women) to allow for a statistical comparison between sexes. Significance for each test will be evaluated with a two-sided alpha,  $p < .05$ .

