**Projected effect size:** Based on preliminary data from our pilot work, we project large within-subject effects across multiple outcomes. We used mean changes in the primary outcome variables, and estimated the standard deviation from the baseline data in our pilot participants or published values using exercise or acute heat exposure as accurate estimates. Effect sizes were calculated as mean change from baseline (control) to post-intervention as follows: Mean arterial pressure  $d = 1.33$ , SDNN (HRV)  $d = 1.03$ , FMD  $d = 1.12$ .

Results will be analyzed using a repeated measures ANOVA (each participant will complete all treatments in a randomized, counterbalanced design) with four trials (Control, Ex, ExHT, HT). Statistical significance will be set at  $\alpha=0.05$  and power at 80%. Secondary analyses using a mixed-model ANOVA design may also be used to examine possible differences in magnitude of change between men and women for each variable. Descriptive statistics will be presented including mean, median, standard deviation, and range.

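### The instruction to avoid exercise and heat during the 24 h recording is written for the control day only, so the nocturnal blood pressure contrasts against control could be biased

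*Combined protocol and SAP*

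**What the plan says.** Section a (Human Subjects Involvement, Characteristics, and Design) describes four trials per participant, "administered in a randomized, counterbalanced fashion, with all participants completing all treatments, with at least 5 days between each trial".

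Section b (Study Procedures, Materials, and Potential Risks) then covers the study days. For Ex + HT, Ex and HT it describes only what happens in the laboratory after the baseline measures. The next sentence concerns the control day: only baseline measures are taken, and the volunteer leaves with an "ambulatory blood pressure cuff with instructions to refrain from exercise or heat exposure during the 24h measurement". The Blood Pressure measurement paragraph gives all four conditions the same recording window: "Ambulatory blood pressure will be measured for a 24 hour period following each of the four conditions". It adds no rule on activity.

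The Leg heating paragraph says that in the HT trial "participants will complete the 45 minute hot (42°C) leg immersion with no prior exercise". That covers the time before the immersion, not the hours after it.

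Statistical Design and Power states: "The primary outcome variable for Specific Aim 1 is mean nocturnal blood pressure". The planned analysis is a repeated-measures ANOVA across the four trials, with control as one level. Nowhere do the documents give an activity rule for the hours after an active session, an activity log or an adherence check.

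**The concern.** The Aim 1 outcome is read from a period in which the participant is at home and unsupervised. The behaviours restricted on the control day, exercise and heat, are the interventions under test. The protocol itself expects both to lower pressure: the Exercise Intervention paragraph says the chosen exercise has reduced systolic and diastolic pressure in hypertensive subjects, and the risk section expects a small fall during heating.

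Suppose some participants train or take a hot bath in the evening after an active session, while on the control day they are told not to. Any resulting fall in overnight pressure would be credited to the assigned session. Counterbalancing the order balances period effects. It cannot balance an instruction that is tied to one condition whenever that condition falls. A larger sample does not remove the bias either.

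**Working it through.** **1. The plan's own figure.** The only figure attached to this outcome is the Aim 1 minimum of 8 participants.
- Inputs from Statistical Design and Power: d = 1.33 (labelled mean arterial pressure; applying it to nocturnal pressure is an assumption), two-sided alpha 0.05, power 80%.
- A paired t-test with the noncentral t distribution gives N = 7.
- A four-level repeated-measures ANOVA with f = d/√8 = 1.33/2.828 = 0.470 and an assumed correlation of 0.5 gives N = 8.

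The stated 8 is reproduced. It does not depend on the activity instruction, so correcting the instruction leaves the sample size as it is.

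**2. The written rules side by side.**

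| Condition | In the laboratory | Written rule for the next 24 h |
|---|---|---|
| Control | baseline measures only | no exercise or heat |
| Ex | walking, then 33°C sham immersion | none stated |
| HT | 42°C immersion | none stated |
| Ex + HT | walking, then 42°C immersion | none stated |

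The written rule differs in three pairs: Ex, HT and Ex + HT, each against control. It is the same within the three pairs of active conditions.

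**3. Form of the bias.** Let q be the share of recordings that contain an extra exposure and D the amount by which that exposure lowers nocturnal pressure. Then

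bias in the apparent reduction = (q_active − q_control) × D.

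The documents give neither q nor D. Assume q_control = 0 (full compliance on control), q_active = 10% to 40%, and D = 3 to 6 mmHg, with the extra exposure having its full effect even after a trial session the same day:
- 0.10 × 3 = 0.3 mmHg
- 0.10 × 6 = 0.6 mmHg
- 0.40 × 3 = 1.2 mmHg
- 0.40 × 6 = 2.4 mmHg

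With one instruction for all four days and equal compliance, q_active = q_control and the bias is zero.

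**4. What a bias does to the test.** Express the bias as b, in SDs of the paired difference. With no true effect, the rejection probability of the two-sided 5% paired t-test follows from a noncentrality of b√N. At the planned N = 20 (10 men, 10 women):
- b = 0.025 (10% of participants, effect 0.25 SD): 0.025 × √20 = 0.112, rejection 5.1%
- b = 0.25 (25% of participants, effect 1.0 SD): 0.25 × √20 = 1.118, rejection 18.6%

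For b = 0.25 at N = 10, the noncentrality is 0.25 × √10 = 0.79 and the rejection probability is 10.9%. A larger sample therefore makes a fixed bias more likely to reach significance. These shares and effects are also assumed.

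**The case against.** The strongest reply is that silence is not permission. The protocol nowhere says that participants may exercise or use heat after an active session. Because control is defined as no exercise or heat exposure, the control-day sentence may simply describe that condition, and staff may give the same instruction every time. This stands in part: differing behaviour is not shown, and a reader who infers that the plan builds it in goes further than the text. What remains is that the text is explicit for one recording and silent for three.

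A reader might also infer that every comparison with control, or every outcome, is affected. The documents do not support that. Heart rate variability and flow-mediated dilation, the Aim 2 and Aim 3 outcomes, are measured in the laboratory. Ex + HT against Ex, which bears most directly on whether heat adds to exercise, has the same written conditions on both sides.

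Nor does it follow that skipping usual exercise after an active session would hide an effect. Exercise is already barred on control, so skipping it makes the two days alike. The absence of pre-visit restrictions applies to all four conditions and creates no inequality between them.

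Finally, the size is wholly assumed. The upper end needs 40% of participants to add an exposure after a trial session while wearing a cuff that inflates hourly, and nothing in the documents supports that rate. A more extreme case, in which half of participants gain an effect of 1.33 SD (b = 0.665), would give 80.5% rejection at N = 20. That should carry no weight: it credits incidental activity with the full projected effect of the combined treatment, and it treats 1.33 as SDs of the paired difference, whereas the plan takes its SD from baseline or published data.

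**Conclusion.** The point holds within limits. As written, the plan restricts exercise and heat in the reference condition and leaves them unaddressed in the three active ones, during the window that supplies the Aim 1 primary outcome. The three nocturnal pressure contrasts against control could be biased, most plausibly towards a larger apparent benefit. The illustrative 0.3 to 2.4 mmHg is a scale, not an estimate. It rests on assumed values of q and D, on no extra exposure on control days, and on an extra exposure keeping its full effect after a session. At the low end the consequence is trivial. The case for acting rests on an asymmetry that can be avoided at almost no cost, not on the upper figure.

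**What to change.** In section b, replace the control-day wording with one instruction that applies to all four recordings: no exercise or heat exposure beyond the assigned session during the 24 h measurement. Put the same sentence on the participant instruction sheet. When the monitor is returned, ask one question on whether any exercise or heat exposure took place, and record the answer by condition.

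The cost is one sentence, one question and a small added restriction on participants on three more days. Sample size, analysis and interventions stay as they are. If staff already give the instruction every day, the change only records existing practice.
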